5.6.2.1. Imputation Rules for Missing Adverse Event Date/Time of Onset

5.6.2.1.1. Treatment-emergent AEs

AEs with completely missing onset dates will be considered as treatment-emergent (avoiding under reporting of treatment-emergent AEs). AEs with partially missing onset dates will also be included as treatment-emergent when the month (if it exists) and the year occur on or later than the month and year of the initial study treatment date.

5.6.2.1.2. Imputation Rules

The date value is split into day, month, and year parts as outlined below:

	Day	Month	Year
Partial AE Start Date	Not used (missing and will be imputed)	MON	YYYY
Treatment Start Date (TRTSDT)	Not used	TRTM	TRTY

Completely missing start dates will not be imputed. Partial AE start dates are imputed with reference to the treatment start date (TRTSDT) as outlined in the matrix of start year (YYYY) vs start month (MON) below.

The *Italic bold* font indicates the imputed values.

	MON MISSING	MON < TRTM	MON = TRTM	MON > TRTM
YYYY MISSING	Do not impute	Do not impute	Do not impute	Do not impute
YYYY < TRTY	(D) = 31DECYYYY Before Treatment Start	(C) = 01MONYYYY Before Treatment Start	(C) = 01MONYYYY Before Treatment Start	(C) = 01MONYYYY Before Treatment Start
YYYY = TRTY	(B) = min(TRTSDT, AE resolution) Uncertain	(C) = 01MONYYYY Before Treatment Start	(B) = min(TRTSDT , AE resolution) Uncertain	(A) = 01MONYYYY After Treatment Start
YYYY > TRTY	(E) = 01JAN YYYY After Treatment Start	(A) = 01MONYYYY After Treatment Start	(A) = 01MONYYYY After Treatment Start	(A) = 01MONYYYY After Treatment Start

The following table is the legend to the matrix above.

Relationship	
Before Treatment Start	Partial date indicates AE start date prior to Treatment Start Date
After Treatment Start	Partial date indicates AE start date after Treatment Start Date
Uncertain	Partial date insufficient to determine the sequence of AE start date and Treatment Start Date
Imputation Calculation	
(A) After Treatment Start	01 MONYYYY (The closest date to the treatment start date for imputation)
(B) Uncertain	min(TRTSDT, AE resolution) (AE happed just after the treatment start)
(C) Before Treatment Start	01MONYYYY (Start-month point will be used for imputation)
(D) Before Treatment Start	31DECYYYY (End-year point will be used for imputation)
(E) After Treatment Start	01JANYYYY (The closest date to the treatment start date for imputation)

Note: Imputation rules for concomitant medications follow the same approach as for AEs. In the case where prior or concomitant medication start/end dates are partial but is required in the calculation of time to first dose (see prior medication under section 6.5) temporary imputed variable(s) will be set earliest/latest possible date for medication start/end dates respectively.

The imputed dates will be used in the calculation of time to first dose but displayed as those were recorded in the listings.

5.6.3. Additional Safety Assessments (if applicable)

5.6.3.1. Clinical Laboratory Tests

Clinical laboratory tests will be displayed for the participants included in the safety analysis set.

Descriptive statistics and graphical displays will be presented for all chemistry, hematology, and urinalysis (pH and specific gravity) laboratory tests at scheduled time points. Week 0 is the Baseline visit for the Clinical Laboratory tests.

Hematology: Platelet Count, Reb blood cell count, Hemoglobin, Hematocrit, RBC Indices: MCV, MCH, %Reticulocytes, White Blood Cell (WBC) count with Differential: Neutrophils, Lymphocytes, Monocytes, Eosinophils, Basophils.

Chemistry: Sodium, Potassium, Chloride, Bicarbonate, Blood urea nitrogen (BUN), Creatinine, Aspartate aminotransferase (AST)/Serum glutamic-oxaloacetic, Alanine aminotransferase (ALT)/ Serum glutamic-oxaloacetic, Gamma- glutamyltransferase (GGT), Bilirubin, Alkaline phosphatase (AP), Creatinine phosphokinase (CP), Lactic acid dehydrogenase (LDH), Uric acid, Calcium, Phosphate, Albumin, Total protein, Cholesterol, HbA1C, hsCRP, Lipid and Metabolic Panel: Triglycerides, Magnesium, Low-density lipoproteins (LDL), High-density lipoproteins (HDL), Very-Low-density lipoproteins (VLDL) (calculated), Non-HDL (calculated), Serum glucose, Serum insulin

Urinalysis: Specific gravity, pH, Glucose, Protein, Blood, Ketones, Bilirubin, Urobilinogen, Nitrite, Leukocytes esterase, Red Blood Cells, White Blood Cells, Epithelial cells, Crystals, Casts, Bacteria, (8-Oxo-7,8-dihyd'o2'-desoxyguanosine) Concentration of oxidative lipid damage [8-Isoprostane] and Malondialdehyde in plasma Concentration of antioxidants (Vitamins C, E).

Screening: Serum and Urine Pregnancy Testing for women of childbearing potential only, Nicotine Dipstick, TB QuantiFERON Test, Serology (HIV antibody, hepatitis B surface antigen [HBsAg], and HCV antibody)

Change from baseline to week of visit will be summarized for chemistry, hematology, and urinalysis (pH, and specific gravity) tests and displayed by week of visit.

Abnormality criteria normal ranges will be applied to baseline and postbaseline values as per the lab reference ranges which will be obtained as an external document.

Postbaseline abnormalities will be compared with their corresponding baseline result:

• For abnormalities based on normal range and/or criteria: If the postbaseline value is above the upper limit and the baseline value is below the upper limit (eg, Normal or Low), then the

postbaseline abnormality will be considered TE. The same applies to the postbaseline value being below the lower limit with the baseline value being above the lower limit (eg, Normal or High).

- For abnormalities based on observed values: If the postbaseline value is observed as abnormal and baseline value is normal (eg., Normal to Abnormal), then the postbaseline abnormality will be considered TE. If the postbaseline value is normal and the baseline value is abnormal (eg., Abnormal to Normal) then the postbaseline abnormality will not be considered TE.
- If the baseline value is missing, a postbaseline abnormality will always be considered as TE.

Number and percentage of participants with treatment-emergent clinically important laboratory values and markedly abnormal treatment emergent values will be presented based on the standard reference ranges provided by the Central Laboratory. A listing of clinically important laboratory values will be provided.

All abnormal laboratory values (out of standard reference range values) will be shared with the clinical team to obtain the flagging for markedly abnormal treatment emergent values.

The clinically important laboratory findings to be reported are described below during any post-baseline visits and not necessarily at the same visits:

- AST (U/L): 3 x ULN
- ALT (U/L): 3 x ULN
- Bilirubin $> 2 \times ULN$ or INR $> 1.5 \times ULN$

Descriptive statistics and change from baseline analyses of clinical laboratory results will be presented.

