Hypersensitivity reactions, including serious hypersensitivity reactions.	Serious hypersensitivity reactions including anaphylaxis have been reported in post-marketing experience with guselkumab in psoriasis patients.	
 
Participants with known allergy, hypersensitivity, or intolerance to guselkumab or its excipients will be excluded from the study.
 
Sites are instructed that before any administration of guselkumab, appropriately trained personnel and medications (eg, injectable epinephrine) must be available to treat hypersensitivity reactions, including anaphylaxis. In addition, all participants must be observed carefully for signs and symptoms of a hypersensitivity reaction (eg, urticaria, pruritis, angioedema, wheezing, dyspnea, or hypotension).
 
Any participant who develops a serious hypersensitivity reaction such as anaphylaxis must discontinue guselkumab (Section 7.1).
 

Malignancy	The preponderance of preclinical data suggests that blockade of endogenous IL-23 would not be detrimental and may in fact be beneficial in tumor immunosurveillance and host protection; however, a risk of malignancy cannot be excluded.	
 
Those participants who currently have a malignancy or have a history of malignancy within 5 years prior to screening (with exceptions noted in Section 5.2) will be excluded from the study.
 
During the conduct of the study, participants will undergo regular clinical monitoring including routine safety labs to assess for any changes in health status that may indicate a possible malignancy.
 
Participants who develop a malignancy during the study (with the exception of no more than 2 localized basal cell skin cancers that are treated with no evidence of recurrence or residual disease) will be discontinued from guselkumab (Section 7.1).
 

Liver injury	A SAE of 'toxic hepatitis' was reported in the ongoing Phase 2/3 guselkumab Crohn's disease program in a participant who received guselkumab 1200 mg IV at Weeks 0, 4, and 8, and 200 mg SC at Week 12. Based on the hepatocellular pattern of injury, temporal relationship of the event to guselkumab exposure, and the exclusion of alternative etiologies, this event may represent drug-induced liver injury possibly related to guselkumab.	Participants with marked liver enzyme elevations or symptoms or signs of liver dysfunction (eg, jaundice), should undergo a thorough investigation for possible causes of liver injury (Section 5.1).

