## Clinical laboratory-related inclusion criteria

The participant

17. Has screening laboratory test results within the following parameters, if one or more of the laboratory parameters is out of range, a single re-test of laboratory values is permitted:

• Hemogle	obin	$\geq$ 10 g/dL	$(SI: \ge 100 \text{ g/L})$
• White b	lood cells	$\geq 3.5 \text{ x } 10^3/\mu\text{L}$	(SI: ≥3.5 GI/L)
• Neutrop	hils	$\geq 1.5 \text{ x } 10^3 / \mu L$	(SI: ≥1.5 GI/L)
• Platelets		${\geq}100~x~10^3/\mu L$	(SI: ≥100 GI/L)
• Serum c	reatinine	$\leq$ 1.5 mg/dL	(SI: $\leq 135  \mu \text{mol/L}$ )

Aspartate aminotransferase (AST), alanine aminotransferase (ALT), and alkaline phosphatase levels must be  $\leq$ 2 × upper limit of normal (ULN) for the laboratory conducting the test.

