6.10. Appendix 10 Laboratory Toxicity Grading

The grading scale use for lab assessments is based on 'Common Terminology Criteria for Adverse Events (CTCAE) v5.0'.

If a laboratory value falls within the grading as specified below but also within the local laboratory normal limits, the value is considered to be normal and will be reset to grade 0.

Pre-baseline measurements will use the same grading ranges as applied to baseline measurements. In case a test has two sets of ranges — one for baseline normal and one for baseline abnormal, the one for baseline normal will be applied for all measurements taken pre-baseline and on baseline.

CTCAE Term	Grade 1	Grade 2	Grade 3	Grade 4	Janssen implementation notes
Blood and lymphatic syst	em disorders				
Anemia	Hemoglobin (Hgb) <lln -="" 10.0="" 100="" 6.2="" <lln="" dl;="" g="" l;="" l<="" mmol="" td="">Hemoglobin (Hgb) <10.0 - 8.0 g/dL; <6.2 - 4.9 mmol/L; <100 - 80g/L	Hemoglobin (Hgb) <8.0 g/dL; <4.9 mmol/L; <80 g/L; transfusion indicated	Life-threatening consequences; urgent intervention indicated	Clinical signs and symptoms are not taken into consideration for grading.	</lln>	Hemoglobin (Hgb) <10.0 - 8.0 g/dL; <6.2 - 4.9 mmol/L; <100 - 80g/L	Hemoglobin (Hgb) <8.0 g/dL; <4.9 mmol/L; <80 g/L; transfusion indicated	Life-threatening consequences; urgent intervention indicated	Clinical signs and symptoms are not taken into consideration for grading.
Leukocytosis	-	-	>100,000/mm3; >100 x 10e9 /L	Clinical manifestations of leucostasis; urgent intervention indicated	Clinical signs and symptoms are not taken into consideration for grading; Added ranges in SI unit (x 10e9 /L)
Investigations			•		
Alanine aminotransferase increased	>ULN - 3.0 x ULN if baseline was normal; 1.5 - 3.0 x baseline if baseline was abnormal	>3.0 - 5.0 x ULN if baseline was normal; >3.0 - 5.0 x baseline if baseline was abnormal	>5.0 - 20.0 x ULN if baseline was normal; >5.0 - 20.0 x baseline if baseline was abnormal	>20.0 x ULN if baseline was normal; >20.0 x baseline if baseline was abnormal	Ranges defined for "abnormal baseline" are applied only if baseline > ULN. If baseline < LLN, then ranges for "normal baseline" are applied.

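### SAP 5.6.3.1 has no treatment-emergent rule for laboratory values that worsen from an already abnormal baseline, and does not say which limit its crossing rule uses

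*SAP*

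**What the plan says.** SAP 5.6.3.1 (Clinical Laboratory Tests) compares each post-baseline abnormality with the Week 0 baseline. The main rule is introduced by the words "For abnormalities based on normal range and/or criteria" and reads: "If the postbaseline value is above the upper limit and the baseline value is below the upper limit (eg, Normal or Low", in which case the abnormality is TE. The low side is the mirror image. A second rule, for abnormalities based on observed values, deals with normal-to-abnormal (TE) and abnormal-to-normal (not TE). A third says: "If the baseline value is missing, a postbaseline abnormality will always be considered as TE".

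The count that depends on these rules is this one: "Number and percentage of participants with treatment-emergent clinically important laboratory values and markedly abnormal treatment emergent values will be presented". The same sentence ties it to the central laboratory's standard reference ranges. The clinically important thresholds are 3x ULN for AST and for ALT, and a bilirubin or INR criterion. Values judged markedly abnormal have no numeric threshold; the clinical team flags them from the out-of-range values.

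Inclusion Criterion 17 of the protocol allows abnormal values at entry: "Aspartate aminotransferase (AST), alanine aminotransferase (ALT), and alkaline phosphatase levels must be" no more than 2x ULN, and haemoglobin need only be at least 10 g/dL. SAP Appendix 10 gives CTCAE grades and, for some tests, two sets of ranges, "one for baseline normal and one for baseline abnormal". Section 5.6.3.1 does not use those grades to define TE.

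**The concern.** A crossing rule identifies new abnormalities and is silent on worsening ones. Someone already beyond the limit at Week 0 cannot cross it again, so even a large deterioration does not meet the definition. The rules are also uneven: an unknown baseline makes every later abnormality TE, while a known abnormal baseline followed by a marked rise does not.

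The liver tests are where this matters most. Protocol 2.3.1 lists liver injury as a potential risk and says of one case elsewhere in the programme that "this event may represent drug-induced liver injury possibly related to guselkumab". A TE count that can omit participants who entered with raised enzymes errs in one direction only, towards fewer events.

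**Working it through.** The plan gives no figure to reproduce here, so the check applies the written rule to example values.

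**Rule.** High side: TE if post > L and (baseline < L or baseline missing). The SAP does not fix L. Two values are possible for ALT: L = 1x ULN (reference limit) and L = 3x ULN (the clinically important criterion in 5.6.3.1).

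**ALT rising to 10x ULN.** Appendix 10 grades the baseline value by the normal-baseline ranges. It grades later values as multiples of baseline when baseline was above ULN: more than 3.0 to 5.0 times is Grade 2, more than 5.0 to 20.0 times is Grade 3.

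| Baseline (x ULN) | TE if L = 1x ULN | TE if L = 3x ULN | Multiple of baseline | Grade: baseline to post |
|---|---|---|---|---|
| 0.8 | yes | yes | graded on ULN | 0 to 3 |
| 1.2 | no | yes | 10/1.2 = 8.3 | 1 to 3 |
| 1.5 | no | yes | 10/1.5 = 6.7 | 1 to 3 |
| 1.9 | no | yes | 10/1.9 = 5.3 | 1 to 3 |
| 2.0 | no | yes | 10/2.0 = 5.0 | 1 to 2 |
| missing | yes | yes | not available | not available |

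For every baseline above 1x and up to 2x ULN, the two readings give opposite answers.

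**Which reading the text favours.** The bracketed examples in the rule are normal or low, which are reference-range categories. The paragraph before the rule applies the laboratory reference ranges to baseline and post-baseline values, and the TE count is itself tied to the standard reference ranges. These point to L = 1x ULN. The words "For abnormalities based on normal range and/or criteria" keep L = 3x ULN open.

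**A test with no numeric criterion.** Haemoglobin 10.0 g/dL meets Inclusion Criterion 17. Assume the laboratory's LLN is above 10.0 g/dL (the documents give no value). Appendix 10 then puts 10.0 in Grade 1 (below LLN down to 10.0) and 7.5 in Grade 3 (below 8.0). Baseline is already below the lower limit, so the fall is not TE. Section 5.6.3.1 states no other limit for haemoglobin, so there is no second reading to rescue it.

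**Would a grade-based rule alone do?** No.
- ALT from 1.5x to 4x ULN is 4/1.5 = 2.7 times baseline, Grade 1 before and after. It newly exceeds 3x ULN, so a criterion rule is needed to catch it.
- Alkaline phosphatase from 2x to 5x ULN is 5/2 = 2.5 times baseline, also Grade 1 before and after.
- Several tests listed in 5.6.3.1, such as LDH, urea nitrogen, uric acid and phosphate, have no grades in Appendix 10, so the crossing rule must stay for them.

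**The case against.** A reader might infer that a participant who enters with raised ALT and reaches 10x ULN disappears from the laboratory output. The documents do not support that, for two reasons.

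First, exclusion from the TE table is not certain. The rule covers criteria as well as normal ranges, and against 3x ULN every eligible ALT baseline is below the limit. The reporting sentence also sets no baseline condition: "The clinically important laboratory findings to be reported are described below during any post-baseline visits and not necessarily at the same visits".

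Second, the value is reported elsewhere. It enters the descriptive and change-from-baseline summaries and the listing of clinically important values, none of which depends on TE status. All out-of-range values go to the clinical team. Protocol 8.2.4 requires clinically relevant laboratory changes to be recorded as adverse events, the adverse event definition in protocol Appendix 13 includes aggravation from baseline, and TEAE status in SAP 5.6.2 depends on timing. With few participants, a listing shows each case.

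Both points stand and limit the concern to one table. They do not remove it. The criterion reading helps only AST, ALT, bilirubin and INR, and the list of clinically important findings covers only those tests. Summary statistics give no count of participants. The cross-tabulation in protocol 9.4.4 is not repeated in SAP 5.6.3.1, and its high-to-high cell would hide the size of a rise. The adverse event route depends on the investigator's judgement of relevance.

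**Conclusion.** The gap is real and should be closed. As written, the TE definition omits worsening from an abnormal baseline and leaves its limit unstated. For ALT baselines above 1x and up to 2x ULN, whether a rise to 10x ULN is counted depends on which limit the programmer picks. For tests without a numeric criterion, worsening is not TE on the only limit stated.

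The consequence is a possible undercount confined to the TE n (%) table. Its size cannot be given: the documents do not report how many participants had abnormal baselines, and the planned 50 no longer applies after early termination. The ALT example needs no assumption beyond the reading of the limit; the haemoglobin example assumes an LLN above 10.0 g/dL. The entry limits apply to screening tests while baseline is Week 0, so baseline values may differ somewhat from those limits. It would go too far to conclude that liver signals are lost from the report.

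**What to change.** In SAP 5.6.3.1, keep the crossing and missing-baseline rules and add that an abnormality is also TE if either:

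- (a) for tests graded in Appendix 10, its CTCAE grade is worse than the baseline grade; or
- (b) for the clinically important criteria (AST or ALT 3x ULN, bilirubin, INR), the post-baseline value meets the criterion and the baseline value did not.

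State that the criterion, not 1x ULN, is the limit for the clinically important table. In the examples above, (a) captures the haemoglobin fall and the ALT rises to 10x ULN from baselines up to 2x ULN, and (b) captures ALT from 1.5x to 4x ULN. Alkaline phosphatase from 2x to 5x ULN would still not be TE, and ungraded tests would still rely on crossing, so the change-from-baseline summaries remain necessary.

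The cost is SAP wording and minor programming on data and a grading table that already exist. Slightly more abnormalities will be reported as TE.

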#### **Serious Adverse Events**

All SAEs occurring during the study must be reported to the appropriate Sponsor contact person by study-site personnel within 24 hours of their knowledge of the event.

Information regarding SAEs will be transmitted to the Sponsor using the Serious Adverse Event Form and Safety Report Form of the CRF, which must be completed and reviewed by a physician from the study-site, and transmitted to the Sponsor within 24 hours. The initial and follow-up reports of a SAE should be transmitted electronically or by facsimile (fax) via a secure transmission system.

Any possible Hy's law case (AST or ALT  $\geq$ 3x ULN together with bilirubin  $\geq$ 2X ULN or INR >1.5) is considered an important medical event and must be reported to the sponsor in an expedited manner using the Serious Adverse Event form, even before all other possible causes of liver injury have been excluded. The INR criterion is not applicable to participants receiving anticoagulants.

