Alkaline phosphatase increased	>ULN - 2.5 x ULN if baseline was normal; 2.0 - 2.5 x baseline if baseline was abnormal	>2.5 - 5.0 x ULN if baseline was normal; >2.5 - 5.0 x baseline if baseline was abnormal	>5.0 - 20.0 x ULN if baseline was normal; >5.0 - 20.0 x baseline if baseline was abnormal	>20.0 x ULN if baseline was normal; >20.0 x baseline if baseline was abnormal	Ranges defined for "abnormal baseline" are applied only if baseline > ULN. If baseline < LLN, then ranges for "normal baseline" are applied.
Aspartate aminotransferase increased	>ULN - 3.0 x ULN if baseline was normal; 1.5 - 3.0 x baseline if baseline was abnormal	>3.0 - 5.0 x ULN if baseline was normal; >3.0 - 5.0 x baseline if baseline was abnormal	>5.0 - 20.0 x ULN if baseline was normal; >5.0 - 20.0 x baseline if baseline was abnormal	>20.0 x ULN if baseline was normal; >20.0 x baseline if baseline was abnormal	Ranges defined for "abnormal baseline" are applied only if baseline > ULN. If baseline < LLN, then ranges for "normal baseline" are applied.
Blood bilirubin increased	>ULN - 1.5 x ULN if baseline was normal; > 1.0 - 1.5 x baseline if baseline was abnormal	>1.5 - 3.0 x ULN if baseline was normal; >1.5 - 3.0 x baseline if baseline was abnormal	>3.0 - 10.0 x ULN if baseline was normal; >3.0 - 10.0 x baseline if baseline was abnormal	>10.0 x ULN if baseline was normal; >10.0 x baseline if baseline was abnormal	Ranges defined for "abnormal baseline" are applied only if baseline > ULN. If baseline < LLN, then ranges for "normal baseline" are applied.

CONFIDENTIAL – FOIA Exemptions Apply in U.S. Status: Approved, Date: 21 July 2023

CTCAE Term	Grade 1	Grade 2	Grade 3	Grade 4	Janssen implementation notes
Cholesterol high	>ULN - 300 mg/dL;	>300 - 400 mg/dL;	>400 - 500 mg/dL;	>500 mg/dL;	•
	>ULN - 7.75 mmol/L	>7.75 - 10.34 mmol/L	>10.34 - 12.92 mmol/L	>12.92 mmol/L	
CPK increased	>ULN - 2.5 x ULN	>2.5 x ULN - 5 x ULN	>5 x ULN - 10 x ULN	>10 x ULN	
Creatinine increased	Creatine Kinase	Creatine Kinase	Creatine Kinase	Creatine Kinase	
	>ULN - 1.5 x ULN	>1.5 - 3.0 x baseline;	>3.0 x baseline;	>6.0 x ULN	
		>1.5 - 3.0 x ULN	>3.0 - 6.0 x ULN		
GGT increased	>ULN - 2.5 x ULN if	>2.5 - 5.0 x ULN if	>5.0 - 20.0 x ULN if	>20.0 x ULN if baseline	Ranges defined for
	baseline was normal;	baseline was normal;	baseline was normal;	was normal;	"abnormal baseline" are
	2.0 - 2.5 x baseline if	>2.5 - 5.0 x baseline if	>5.0 - 20.0 x baseline if	>20.0 x baseline if	applied only if baseline >

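### SAP Appendix 10 names creatine kinase in the creatinine grading row, and the SAP 5.6.3.1 liver list does not identify the protocol's possible Hy's law combination (minor, descriptive safety outputs only)

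*SAP*

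**What the plan says.** **Liver criterion, protocol.** Section 8.3.1 (Serious Adverse Events) defines a possible Hy's law case as AST or ALT at least "3x ULN together with bilirubin" at least "2X ULN or INR >1.5) is considered an important medical event". It must be sent to the sponsor on the SAE form in an expedited manner. The section adds: "The INR criterion is not applicable to participants receiving anticoagulants". Protocol Appendix 2 repeats the definition and the exemption.

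**Liver criterion, SAP.** Section 5.6.3.1 promises counts, percentages and a listing of clinically important laboratory values. "The clinically important laboratory findings to be reported are described below", it says, "during any post-baseline visits and not necessarily at the same visits". Three bullets follow: AST 3 x ULN; ALT 3 x ULN; and bilirubin >2 x ULN or INR >1.5 x ULN. The term Hy's law does not appear. SAP Appendix 2, which lists changes from the protocol's planned analyses, does not mention the difference.

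**Toxicity grading, SAP.** Appendix 10 has a row labelled "Creatinine increased" in which all four grade cells name creatine kinase. The row directly above it, for CPK, has other limits. The INR row of the same appendix uses absolute cut-offs of 1.2, 1.5 and 2.5 for participants not on anticoagulation.

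**The concern.** Creatine kinase is a muscle enzyme and serum creatinine is a renal marker. If the Appendix 10 row were programmed as written, renal toxicity grades would come from the wrong analyte. Both analytes are in the chemistry panel drawn at Screening Visit S1 and at every dermatology visit from Week 0 to Week 40, so the row would apply to routine data. The SAP also mixes the two names elsewhere: the chemistry list in 5.6.3.1 gives creatinine phosphokinase where the protocol has creatine phosphokinase. A programmer therefore cannot rely on the rest of the SAP to settle which is meant.

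For the liver list, the analytes and multipliers are those of the protocol's Hy's law rule, but the link between them is missing. The wording about different visits has little purpose unless items are combined, while the bullets read as separate items. Two programmers could produce different tables. Liver injury is a named potential risk in protocol 2.3.1, so a table that isolates the protocol's combination is a reasonable thing to expect.

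**Working it through.** The plan states no figure here to reproduce. The check sets the texts side by side and applies each rule to example values.

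**1. Creatinine row against CPK row (SAP Appendix 10)**

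Inputs, in multiples of ULN:
- CPK row: Grade 1 above 1 to 2.5, Grade 2 to 5, Grade 3 to 10, Grade 4 above 10.
- Creatinine row: Grade 1 above 1 to 1.5, Grade 2 to 3.0, Grade 3 to 6.0, Grade 4 above 6.0. This row also has multiples of baseline for Grades 2 and 3. They are left out here; read as alternatives, they could only raise a grade.

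| Creatine kinase, x ULN | CPK row | Creatinine row, read literally |
|---|---|---|
| 2 | Grade 1 | Grade 2 |
| 4 | Grade 2 | Grade 3 |
| 7 | Grade 3 | Grade 4 |
| 11 | Grade 4 | Grade 4 |

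No other row grades serum creatinine.

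**2. Liver criterion, line by line**

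| Element | Protocol 8.3.1 | SAP 5.6.3.1 |
|---|---|---|
| AST or ALT | ≥3 x ULN | 3 x ULN, no operator |
| Link to bilirubin/INR | required together | separate bullets |
| Bilirubin | ≥2 x ULN | >2 x ULN |
| INR | >1.5 (absolute) | >1.5 x ULN |
| Timing | no visit window stated | any post-baseline visits, not necessarily the same |
| Anticoagulant exemption | yes | not repeated |

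**3. INR scale**

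SAP cut = 1.5 x ULN. The documents give no ULN for INR, so a range is assumed:
- ULN 1.0: 1.5 x 1.0 = 1.50, the same as the protocol.
- ULN 1.1: 1.5 x 1.1 = 1.65.
- ULN 1.2: 1.5 x 1.2 = 1.80.
- ULN 1.3: 1.5 x 1.3 = 1.95.

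Values above 1.5 and up to that cut meet the protocol's INR limit but not the SAP's. With a ULN of 1.1 or 1.2, an INR of 1.6 off anticoagulation is Grade 2 in SAP Appendix 10 yet not clinically important in SAP 5.6.3.1.

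**4. What each reading of the SAP list does with a protocol case**

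*Separate items.* Every protocol case has AST or ALT ≥3 x ULN. If the SAP's 3 x ULN means ≥3, the AST or ALT bullet flags every one and none is missed. If it means >3, the only cases lost have the higher of AST and ALT at exactly 3.0 x ULN, with bilirubin and INR also not above the SAP limits. The cost is over-inclusion: ALT 5 x ULN with normal bilirubin and INR is flagged as well, and nothing marks the combination.

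*Combined items, with ≥3 for AST/ALT.* Missed cases are those with bilirubin exactly 2.0 x ULN and no INR trigger, and, when the ULN exceeds 1.0, those resting only on an INR inside the gap. Example: ALT 5 x ULN, bilirubin 1.0 x ULN, INR 1.6 with ULN 1.1 is a protocol case, but 1.6 is below 1.65, so it is not flagged. ALT 5 x ULN at one visit and bilirubin 3 x ULN at a much later one would count.

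**5. How often the INR item can operate**

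INR is not listed in the hematology or chemistry panels of protocol Appendix 2, nor in the SAP's chemistry list. The difference in scale therefore reaches only INR results obtained outside the scheduled tests. The exemption is also narrow in practice, since protocol Table 1 prohibits vitamin K antagonists.

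**The case against.** The strongest reply is that the two liver texts serve different purposes. Protocol 8.3.1 is an expedited reporting rule for sites. SAP 5.6.3.1 is a list of single laboratory findings for a summary and a listing, and it does not claim to restate Hy's law. That stands. Cases reported by sites reach the sponsor by the SAE route, and SAP 5.6.2 lists all SAEs.

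A reader might infer that the SAP tables would flag the wrong results or miss reportable cases. The documents do not support that. On the separate-items reading the list is a wider screen that catches essentially every protocol case; what it lacks is a marker for the combination. Nor is the different-visits wording a proven contradiction, because the protocol says the elements occur together but sets no window.

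A reader might also infer that creatinine toxicity counts will be false. This is not established either. The row label is correct, CPK has its own row, and the cell text looks like a wrong analyte name. Section 5.6.3.1 names no table of toxicity grades, and the table shells are in a separate Data Presentation Specifications document. Creatinine is still summarised and compared with its reference range.

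What the reply does not remove is that the row is wrong as written, that the liver list can be read in two ways, and that the SAP uses two INR scales.

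**Conclusion.** Both defects are in the current text, and both are minor. The Appendix 10 row names the wrong analyte; misgrading follows only if the row is programmed literally and grades are tabulated. The 5.6.3.1 list does not identify the protocol's possible Hy's law combination and leaves the operators, the INR scale, the visit window and the anticoagulant exemption either unstated or different from the protocol.

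The effect is confined to descriptive safety outputs in a study stopped early with few participants. No efficacy analysis is touched. The size of the INR gap rests on an assumed ULN above 1.0; at 1.0 it vanishes. The bilirubin difference matters only at exact equality. The conclusion that few cases would be lost rests on reading the list as separate items.

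**What to change.** 1. In SAP Appendix 10, replace creatine kinase with serum creatinine in the four cells of the creatinine row, and correct the CPK name in the 5.6.3.1 chemistry list.
2. In SAP 5.6.3.1, keep the single-item AST, ALT and bilirubin findings and state their operators. Replacing them with the combination alone would drop isolated elevations that the SAP now reports.
3. Add a separate flag for the protocol-defined combination. Before programming it, reconcile 5.6.3.1 with protocol 8.3.1 and Appendix 2 on the operators, the INR scale, the visit window and the anticoagulant exemption. Bring the INR scale into line with SAP Appendix 10 as well. Which limits apply is for the sponsor to settle.
4. Record any remaining difference from the protocol in SAP Appendix 2.

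The cost is SAP wording and two derivations. No new data are needed.
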